6.1. Primary analysis

• Treatment effects on the transfer task (n-back task) at post-assessment will be analyzed using a linear mixed-effects model. This model will include the n-back performance at post- and follow-up assessments (percentage of correct responses) as the dependent variable. Fixed effects will include group (cognitive training vs. PMR), measurement time point (post vs. follow-up) and task difficulty (1-back vs. 2-back). Control covariates will include the n-back performance at pre-assessment (percentage of correct responses), age, and sex. A random intercept for subjects will also be included. The primary outcome (immediate transfer effects at post-assessment) will be estimated via marginal means (95% CI) from this model.

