5. Handling of missing values

In cases of missing data and assuming the data are missing at random (MAR) or completely at random (MCAR), multiple imputation will be used to estimate the missing values with 30 imputed datasets.

6. Statistical analyses

For all outcomes and time points, we will present appropriate descriptive statistics (mean, standard deviation, median, interquartile range, and absolute and relative frequencies) depending on the scale and distribution of each outcome variable in total (only at preassessment) and by group. The statistical analyses will evaluate the immediate treatment effects at post-assessment (V11) and the sustained treatment effects at the one-month follow-up assessment (V12). In the secondary analyses, we will compare the cognitive training and groups, as well as the cognitive training groups receiving active versus sham tDCS.

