6.2. Secondary analyses

Effects of cognitive training vs. PMR

- Treatment effects on the transfer task (n-back task) at follow-up assessment will be examined by estimating marginal means (and 95% CI) from the model above.
- Treatment effects on the training task (letter updating task) at post- and follow-up assessments will be analyzed using a linear mixed-effects model. This model will include the letter updating performance at post- and follow-up assessments (number of correctly recalled lists) as the dependent variable. Fixed effects will include group (cognitive training vs. PMR) and measurement time point (post vs. follow-up). Control covariates will include the letter updating performance at pre-assessment (number of correctly recalled lists), age, and sex. A random intercept for subjects will also be included. Immediate and sustained training effects at post- and follow-up assessments will be estimated via marginal means (95% CI) from this model.
- Treatment effects on the visuospatial memory task (virtual reality task) at post- and followup assessments will be analyzed using a linear mixed-effects model. This model will include the virtual reality task performance at post- and follow-up assessments (number of goals reached) as the dependent variable. Fixed effects will include group (cognitive training vs. PMR) and measurement time point (post vs. follow-up). Control covariates will include the virtual reality task performance at pre-assessment (number of goals reached), age, and sex. A random intercept for subjects will also be included. Immediate and sustained effects on visuospatial memory performance at post- and follow-up assessments will be estimated via marginal means (95% CI) from this model.
- Treatment effects on working memory discrimination (n-back task d'prime scores) at postand follow-up assessment will be analyzed using a linear mixed-effects model. This model will include the n-back d'prime scores at post-and follow-up assessments as the dependent variable. Fixed effects will include group (cognitive training vs. PMR), measurement time point (post vs. follow-up) and task difficulty (1-back vs. 2-back). Control covariates will include the n-back d'prime scores at pre-assessment, age, and sex. A random intercept for subjects will also be included. Immediate and sustained effects on working memory discrimination at post- and follow-up assessments will be estimated via marginal means

(95% CI) from this model.

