- Treatment effects on health-related quality of life (PROMIS® PROPr scores) at post- and follow-up assessment will be analyzed using a linear mixed-effects model. This model will include the PROMIS® PROPr scores at post-and follow-up assessments as the dependent variable. Fixed effects will include group (cognitive training vs. PMR) and measurement time point (post vs. follow-up). Control covariates will include the PROMIS® PROPr scores at pre-assessment, age, and sex. A random intercept for subjects will also be included. Immediate and sustained effects on health-related quality of life at post- and follow-up assessments will be estimated via marginal means (95% CI) from this model.
- Treatment effects on subjective cognitive functioning (PROMIS® T-scores) at post- and follow-up assessment will be analyzed using a linear mixed-effects model. This model will include the PROMIS® cognitive functioning T-scores at post-and follow-up assessments as the dependent variable. Fixed effects will include group (cognitive training vs. PMR) and measurement time point (post vs. follow-up). Control covariates will include the PROMIS® cognitive functioning T-scores at pre-assessment, age, and sex. A random intercept for subjects will also be included. Immediate and sustained effects on subjective cognitive functioning at post- and follow-up assessments will be estimated via marginal means (95% CI) from this model.
- Treatment effects on the post-COVID functional status (PCFS total raw scores) at post- and follow-up assessment will be analyzed using a linear mixed-effects model. This model will include the PCFS total raw scores at post-and follow-up assessments as the dependent variable. Fixed effects will include group (cognitive training vs. PMR) and measurement time point (post vs. follow-up). Control covariates will include the PCFS total raw scores at pre-assessment, age, and sex. A random intercept for subjects will also be included. Immediate and sustained effects on post-COVID functional status at post- and follow-up assessments will be estimated via marginal means (95% CI) from this model.

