- Treatment effects on the sleep efficiency levels (sleep efficiency percentage) at postassessment will be analyzed using a linear mixed-effects model. This model will include the sleep efficiency percentage at post-assessment as the dependent variable. Fixed effects will include group (cognitive training vs. PMR). Control covariates will include the sleep efficiency percentage at pre-assessment, age, and sex. A random intercept for subjects will also be included.

Effects of cognitive training with active vs. sham tDCS

We will use the same analytical approach to assess the effects of active versus sham tDCS on all outcomes, replacing the group effect (cognitive training vs. PMR) with the stimulation group variable (active vs. sham tDCS). The only exception will be the analysis of treatment effects on the training task (letter updating task), which will be examined using the following two linear mixed-effects models:

• The first model will assess the treatment effects on the training task (letter updating task) at training- and post- assessments. This model will include the letter updating performance across all training and post-assessments (number of correctly recalled lists in sessions from V2 to V11) as the dependent variable. Fixed effects will include the stimulation group (active vs. sham tDCS) and measurement time point (V2 to V11). Control covariates will include

the letter updating performance at pre-assessment (number of correctly recalled lists), age, and sex, along with a random intercept for subjects. Training and immediate post-assessment effects will be estimated through marginal means (95% CI) from this model.

• The second model will evaluate the treatment effects on the training task (letter updating task) at follow-up assessment. This model will include the letter updating performance at post- and follow-up assessments (number of correctly recalled lists) as the dependent variable. Fixed effects will include group (active vs. sham tDCS) and measurement time point (post vs. follow-up). Control covariates will include the letter updating performance at pre-assessment (number of correctly recalled lists), age, and sex. A random intercept for subjects will also be included. Sustained training effects at follow-up assessment will be estimated via marginal means (95% CI) from this model.

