The choice of link function (logistic, linear, or ordinal) for all analyses will depend on the scale of the dependent variable. For skewed continuous data, we will apply appropriate transformations before analysis. In case of missing values, all secondary analyses will be done using the full analysis set with multiple imputed data. Per-protocol analyses will be conducted as sensitivity analyses. All secondary analyses will be conducted within an exploratory framework.

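### The primary mixed model lists no group-by-time-point interaction, so as written its effect at post-assessment is the post/follow-up average and equals its follow-up effect

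*SAP*

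**What the plan says.** SAP Section 4.1 and footnote d of Table 1 place the primary outcome at post-assessment only. The opening of SAP Section 6 says that the analyses will "evaluate the immediate treatment effects at post-assessment (V11) and the sustained treatment effects at the one-month follow-up assessment (V12"), as two separate questions.

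Section 6.1 then puts the post and follow-up n-back scores into one linear mixed model: "Fixed effects will include group (cognitive training vs. PMR), measurement time point (post vs. follow-up) and task difficulty (1-back vs. 2-back"). The covariates are pre-assessment score, age and sex, with a random intercept for subjects. The primary result is read off as follows: "The primary outcome (immediate transfer effects at post-assessment) will be estimated via marginal means (95% CI) from this model".

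Section 6.2 takes the treatment effect on the same task "at follow-up assessment will be examined by estimating marginal means (and 95% CI) from the model above". The other two-time-point models in Section 6.2 have the same form and make the same promise, for example: "Immediate and sustained effects on health-related quality of life at post- and follow-up assessments will be estimated via marginal means". In the active versus sham comparison, the first letter-updating model covers ten visits: "Fixed effects will include the stimulation group (active vs. sham tDCS) and measurement time point (V2 to V11"). Its output is described as: "Training and immediate post-assessment effects will be estimated through marginal means (95% CI) from this model". Of Section 6.2 as a whole the SAP says: "All secondary analyses will be conducted within an exploratory framework".

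**The concern.** A model with additive group and time-point terms assumes that the treatment effect is the same at every visit. Marginal means by visit then separate the levels of the two groups over time, but not the difference between the groups. The result reported for post-assessment would be a pooled effect over post and one-month follow-up under another name, and the sustained-effect hypothesis in Section 1.3 could not be answered separately.

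This matters most for the primary analysis. It is the only analysis that the SAP does not place in an exploratory framework, and the sample size in Section 1.4 rests on it. If the effect fades after training, the post effect is understated; if it appears late, the post effect is overstated and may be declared when there is none.

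**Working it through.** **1. The plan's own figure.** Section 1.4 gives d = 0.8, two-sided alpha 0.05, power of at least 80%, and 40 versus 20 participants. A noncentral-t calculation needs 19.06 PMR participants, so 20, with 40 in training. The total is 60 and the power 81.9%. The figure is reproduced and is not in dispute.

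**2. Algebra of the listed model.** Write y = b0 + bG·group + bT·time + bD·difficulty + covariates + u_i. The training-minus-PMR difference in marginal means is

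- at post: (b0 + bG) − b0 = bG
- at follow-up: (b0 + bG + bT) − (b0 + bT) = bG

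There is one coefficient and one confidence interval for both visits. With every subject observed at both visits, bG is the simple mean of the two visit-specific effects. Each imputed data set meets that condition.

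**3. Check by fitting.** Data were simulated for 40 versus 20 subjects, two visits and two difficulty levels, with the Section 6.1 covariates and assumed variances. There were 60 replicates per scenario. The post and follow-up contrasts of the additive model differed by at most 3e-16. In complete data, bG differed from the mean of the two interaction-model effects by at most 8e-15.

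| True post / follow-up | Additive model, both visits | Interaction model, post / follow-up |
|---|---|---|
| 0.8 / 0.4 | 0.60 | 0.82 / 0.38 |
| 0.8 / 0 | 0.40 | 0.82 / −0.02 |
| 0 / 0.8 | 0.42 | −0.01 / 0.84 |

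With 15% of follow-up missing and not imputed, the two contrasts were still identical, but the average leaned towards post (0.8 / 0 gave 0.45).

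**4. Size.** Assumptions, none of them from the SAP: SD 1 at each visit; equal correlation r between pre, post and follow-up; baseline adjustment; 55 degrees of freedom (60 subjects minus intercept, group, baseline, age and sex). The base case is r = 0.6; brackets give r = 0.4 to 0.8.

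- V11 contrast: residual variance 1 − r² = 0.64; SE = √(0.64 × (1/40 + 1/20)) = 0.219; 0.8/0.219 = 3.65; power 95% (88–99.8%).
- Model as written: residual variance (1 + r)/2 − r² = 0.80 − 0.36 = 0.44; SE = √(0.44 × 0.075) = 0.182.

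| True post / follow-up | Reported as post effect | Effect/SE | Probability of rejection |
|---|---|---|---|
| 0.8 / 0.8 | 0.80 | 4.40 | 99% |
| 0.8 / 0.4 | 0.60 | 3.30 | 90% (83–99%) |
| 0.8 / 0.2 | 0.50 | 2.75 | 77% (68–94%) |
| 0.8 / 0 (extreme) | 0.40 | 2.20 | 58% (50–80%) |
| 0 / 0.2 | 0.10 | 0.55 | 8% (8–11%) |
| 0 / 0.4 | 0.20 | 1.10 | 19% (16–29%) |
| 0 / 0.8 (extreme) | 0.40 | 2.20 | 58% (50–80%) |

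The averaged contrast loses power only when follow-up keeps less than 2·√(0.44/0.64) − 1 = 66% (60–70%) of the post effect.

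**5. The V2 to V11 model.** Ten visits are pooled. If the effect at V11 is D, the reported effect is D/10 when it exists only at V11, 0.5 D when it rises linearly from zero at V2, and D only when it is constant.

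**6. Standard error once the interaction is added.** The n-back models have two difficulty scores per visit. Let s, v, d and e be the subject, subject-by-visit, subject-by-difficulty and residual variances. With balanced data, a subject's mean at V11 has variance s + v + d/2 + e/2. A model with only a random intercept estimates s + 2v/3 + 2d/3 + e/2. The shortfall is v/3 − d/6, which is positive when d < 2v. In simulations with d = 0, the type I error of the V11 contrast was 6.2% at v = 0.2 (s = 0.6, e = 0.4) and up to 7.9% over other variance splits. A subject-by-visit effect brought it to 4.5–4.8%.

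**The case against.** The strongest reply is that this is incomplete wording and not a wrong analysis. The listed fixed effects are not said to be exhaustive, and asking for separate immediate and sustained effects makes sense only with an interaction. That may well be what the authors intend. But an SAP fixes the model before the data are seen, and this one spells out the terms model by model without ever naming an interaction. Two analysts could follow it faithfully and report different primary estimates.

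Four narrower points stand in part:

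- There is no bias if the effect is the same at both visits, and above about two-thirds retention the averaged contrast has more power. It still answers a different question.
- Section 6.2 allows other link functions and transformations. Back-transformed differences could then vary by visit, but through the link and not through a visit-specific treatment effect. The finding is therefore stated on the model scale.
- The SAP does not call the primary analysis confirmatory, and Section 6.1 names a confidence interval but no test. The power figures apply the two-sided 0.05 level of Section 1.4.
- The need for a subject-by-visit effect depends on variances that the SAP does not give. At v = 0.2, type I error with a random intercept alone fell from 6.0% to 5.3% and 4.7% as d rose from 0 to 0.2 and 0.4. With the extra term it stayed at 4.1–5.3% in every setting checked, so the term protects without harm.

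**Conclusion.** The concern holds, and it must be fixed because it affects the primary result. Fitted as listed, the Section 6.1 model does not estimate the effect at post-assessment unless the effects at the two visits happen to be equal. The equality of the two contrasts is exact on the model scale and needs no assumption about variances. That they equal the simple average is exact for complete or imputed data.

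The error in the post estimate is half the gap between the visit effects, in either direction. Its consequence for power or false rejection depends on assumed correlations and follow-up effects. It is modest if half the effect persists, and large only if the effect vanishes by follow-up or appears only then. The models in Section 6.2 share the defect but are exploratory, so there it is a matter of matching wording.

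**What to change.** - **Primary model (Section 6.1).** Add the group-by-time-point interaction. Define the primary result as the between-group difference in marginal means at V11, with its 95% CI and a two-sided test at 0.05. Define the follow-up result as the same contrast at V12.
- **Both n-back models (percentage correct and d-prime).** Add a subject-by-visit random effect, so that the V11 standard error does not depend on there being little visit-level variation. Models with one score per visit need no such change.
- **Exploratory models (Section 6.2).** Add group by time point to each two-time-point model, with group meaning training versus PMR or active versus sham. Add stimulation group by visit to the V2 to V11 letter-updating model.

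The cost is about one sentence of wording per model, with no new data and no change to the 60 participants. If the effect is truly constant, the V11 contrast is less precise than the average: about 95% against 99% power at 0.8 SD and correlation 0.6, still above the planned 80%.

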1.1. Study design

This study is a monocentric, prospective, randomized, open-blinded endpoint (PROBE) (17) phase II clinical trial designed to evaluate the effectiveness of a cognitive training intervention compared to a control intervention [Progressive Muscle Relaxation; PMR (18)] in patients with post-COVID subjective or objective cognitive impairment (primary endpoint).

Patients with post-COVID cognitive impairment participate in a three-week intervention program consisting of nine sessions (three per week) of either cognitive training or PMR (18) (open-label interventions). In the cognitive training group, participants are further divided into two subgroups: half receive anodal tDCS while the other half receive sham tDCS in a double-blinded, sham-controlled manner (secondary endpoint). Thus, participants are randomly allocated to one of three study arms: (1) cognitive training with anodal tDCS over the left dorsolateral prefrontal cortex (DLPFC); (2) cognitive training with sham tDCS over the left DLPFC; or (3) PMR with sham tDCS.

Random allocation to these three groups is done through a stratified block randomization method with variable block length, using a 1:1:1 ratio. The stratification is based on participants' performance in the n-back task during pre-assessment, with two strata: those scoring $\leq 87\%$ correct and those scoring > 87% correct. The randomization sequences are generated software's blockrand package using the R (https://CRAN.Rproject.org/package=block- rand; http://www.R-project.org). Following a telephone screening and baseline assessment, eligible participants who provide written informed consent are randomly assigned to a study arm according to the generated randomization sequence within each block and performance stratum.

Secondary hypotheses related to the comparison of the two cognitive training arms with active or sham tDCS, will be evaluated in a double-blinded, sham-controlled manner.

[figure not shown]

Figure 1. Neuromod-COV study flowchart. tDCS: transcranial direct current stimulation; PMR: Progressive Muscle Relaxation. Obtained from Neuromod-COV study protocol (14).

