1.4. Sample size calculation

The power calculation is based on recent studies using multi-session cognitive training interventions compared to control training (19–21), focusing on immediate performance in the trained task. Based on these findings, we estimated an effect size of Cohen's d = 0.8. To detect an effect in the primary outcome (percentage of correct responses on the n-back task between the cognitive training and control PMR groups) using an independent t-test with a two-sided significance level of $\alpha = 0.05$ and a power of at least 80%, 60 participants are required. This includes 40 participants for the cognitive training groups (for secondary comparisons of training combined with anodal vs. sham tDCS) and 20 participants for the PMR group. Even though we intend to analyze the primary outcome using covariance models, a conservative t-test approach was chosen for the power calculation. The sample size was estimated using the R software's *pwr* package (https://cran.r-project.org/package=pwr, http://www.R-project.org). This monocentric clinical trial will enable us to calculate the sample size for a subsequent multicenter clinical trial applying tDCS-accompanied cognitive training.

2. Analysis sets

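### A lone random intercept sets the within-person covariance in the n-back and V2–V11 models, so CIs for visit-specific contrasts may be too narrow or too wide

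*SAP*

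**What the plan says.** SAP section 6.1 models n-back accuracy at post-assessment and follow-up together. Besides group, the fixed factors are "measurement time point (post vs. follow-up) and task difficulty (1-back vs. 2-back"), which gives 2 × 2 = 4 values per person. The covariates are pre-assessment score, age and sex. On dependence within a person it says only: "A random intercept for subjects will also be included". The primary result, the effect at post-assessment (V11), is to be read from this model as marginal means with 95% CIs. Section 6.2 takes the follow-up effect from the same model and repeats the structure for d-prime.

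For active versus sham tDCS, section 6.2 models the letter updating task over V2 to V11, ten values per person, "along with a random intercept for subjects". Effects during training and at V11 are again to come from marginal means.

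The SAP names no random slope, person-by-visit or person-by-difficulty effect, residual covariance structure, unequal visit variance, robust standard error or degrees-of-freedom method. Group and time are listed as main effects, with no group-by-time term. Section 5 plans multiple imputation, so each analysed dataset is complete.

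**The concern.** A random intercept alone treats every pair of a person's values as equally correlated and every visit as equally variable. Two n-back scores from one sitting would then be no more alike than scores taken a month apart. Scores at the same difficulty would be no more alike than scores at different difficulties. In the training model everyone would improve at the same rate, apart from noise. None of this is assured. Table 1 of the SAP itself schedules an initial state questionnaire at each visit, so day-to-day state was thought worth recording.

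The SAP wants effects at particular visits. For such effects the standard error depends on how variance divides between visits, and that is what the restriction fixes. At stake is the coverage of the CI for the declared primary time point and for the immediate effect on the trained task.

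**Working it through.** **The plan's own figure.** Section 1.4 assumes "we estimated an effect size of Cohen's d = 0.8", 40 in cognitive training "and 20 participants for the PMR group", two-sided α = 0.05, and concludes: "a power of at least 80%, 60 participants are required". The noncentrality is 0.8 × √(40 × 20 / 60) = 2.92 on 58 df, giving 81.9% power. With 38 versus 19 power is 79.9%, so 60 is the smallest 2:1 total that reaches 80%. The figure is reproduced. It rests on a t-test and does not depend on this point.

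**Inputs for the check.** Group sizes are 40 versus 20 for n-back, and 20 versus 20 for active versus sham (allocation "using a 1:1:1 ratio"). The SAP gives no variance components, so all those below are assumptions, read as residual to the covariates. Write B for between-person, S for person-by-visit, L for person-by-difficulty and E for residual variance.

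**n-back contrast at V11, group-by-time term included.**

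- The three within-person contrasts have expected mean squares E + 2S (visit), E + 2L (difficulty) and E (their interaction). The random-intercept model pools them into a residual variance of E + (2/3)(S + L).
- The variance of a person's overall mean is B + S/2 + L/2 + E/4. Subtracting a quarter of the fitted residual leaves a fitted intercept variance of B + (S + L)/3.
- Fitted variance of a person's V11 mean: B + (2/3)(S + L) + E/2.
- True variance: B + S + L/2 + E/2.
- Fitted minus true: −S/3 + L/6. The CI is too narrow if S exceeds L/2, too wide if S is below L/2, and exact if they are equal (including both zero).

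| B, S, L, E | Fitted | True | SE ratio | Simulated coverage |
|---|---|---|---|---|
| 0.5, 0, 0, 0.5 | 0.750 | 0.750 | 1.00 | 95.1% |
| 0.5, 0.2, 0, 0.3 | 0.783 | 0.850 | 0.96 | 94.1% |
| 0.4, 0.2, 0.2, 0.2 | 0.767 | 0.800 | 0.98 | 94.6% |
| 0.2, 0.5, 0, 0.3 (extreme) | 0.683 | 0.850 | 0.90 | 92.4% |
| 0.3, 0, 0.4, 0.3 | 0.717 | 0.650 | 1.05 | 96.1% |

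The SE ratio is √(fitted/true). Coverage is from 20,000 simulated trials per scenario. A 2-back residual variance nine times the 1-back value changes nothing (ratio 1.00, coverage 95.0%).

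Unequal visit variances matter more. With components 0.5, 0.1, 0.1, 0.3 and the V11/V12 variance ratio varied:

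| V11/V12 variance ratio | SE ratio | Simulated coverage |
|---|---|---|
| 0.5 | 1.20 | 98.0% |
| 1.5 | 0.90 | 92.2% |
| 2 | 0.85 | 90.2% |
| 3 | 0.80 | 88.4% |

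**n-back exactly as listed, without group-by-time.**

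- The group contrast is a difference in person means, and its variance is the between-person mean square. Simulated coverage is 94.7–95.3% in every scenario.
- The V11 marginal mean of a single group also carries half the common visit difference. Its true variance is (B + S/2 + L/2 + E/4)/n + (S/2 + E/4)/60. The fitted version has [E + (2/3)(S + L)]/240 as its second term.
- With (0.1, 0.4, 0, 0.5) and n = 40: true 0.425/40 + 0.325/60 = 0.01604; fitted 0.425/40 + 0.767/240 = 0.01382; SE ratio 0.93.
- With (0.1, 0.1, 0.6, 0.3) and n = 40: true 0.525/40 + 0.125/60 = 0.01521; fitted 0.525/40 + 0.767/240 = 0.01632; SE ratio 1.04.

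**V2–V11 contrast at V11, group-by-time term included.** A random-intercept fit gives each visit the average of the ten visit variances, so the SE ratio at V11 is √(average variance / V11 variance).

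- Serial correlation, AR(1) with ρ from 0.6 to 0.9 and constant variance: ratio 1.00, coverage 94.7–95.3%.
- Random slopes, with variance at session t equal to 1 + (f − 1)t²/81 for t = 0 to 9. Since Σt² = 285, the average is 1 + 0.352(f − 1). For f = 2: √(1.352/2) = 0.82, coverage 89.1%. For f = 4: √(2.056/4) = 0.72, coverage 84.0%.
- Ceiling, with variance falling linearly to half: √(0.75/0.5) = 1.22, coverage 98.3%.

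**Comparator.** An unstructured covariance, which in complete data without covariates equals a V11-only analysis, gave 94.7–95.3% in every scenario.

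**The case against.** The strongest reply is that the fixed effects as listed contain no group-by-time term. The estimated group effect is then the same at V11 and V12, and its CI is valid in balanced data whatever the within-person covariance. This stands for the contrast. It does not settle the matter. Such a contrast is not specific to post-assessment, which is the declared primary outcome. The CIs of the V11 marginal means are somewhat affected even so. The restriction also reaches the contrast as soon as the needed interaction is added.

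Second, the n-back error is usually small. When person-by-visit and person-by-difficulty variance are both present they partly cancel, as in the 0.98 row above. This also stands.

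Third, a subject random intercept is a common choice with 40 to 60 participants, and richer structures may fail to converge. That is a reason to name a fallback, not to leave the restriction without one.

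A reader might infer that the V11 CIs are simply wrong, or that in the V2–V11 model they must be too narrow because variance grows with learning. The SAP supports neither. It gives no variance components and no information on whether variance grows or shrinks over sessions, and a ceiling would make the CI too wide.

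**Conclusion.** The point holds in a limited form. The SAP commits its repeated-measures models to equal variances and equal correlations, with no alternative planned, while asking for visit-specific effects. With a group-by-time term, the n-back V11 standard error would be about 10% too small to 5% too large under equal visit variances (coverage 92.4–96.1%), and further off if V11 and V12 variances differ. In the V2–V11 model the error can be material in either direction, but section 6.2 labels all secondary analyses exploratory. Serial correlation alone does little.

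The sizes rest on assumed components, complete data, no covariates and no between-imputation variance. They show what could happen, not what will. The group effect averaged over visits and the sample size of 60 are not touched.

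**What to change.** - State the group-by-time term in each model from which separate visit effects are to be read. Changing the covariance alone would not make the contrast visit-specific.
- For n-back accuracy and d-prime, use an unstructured covariance over the four visit-by-difficulty cells. This also allows V11 and V12 variances to differ, which person-by-visit and person-by-difficulty intercepts alone would not.
- For V2–V11, add a random slope for session or allow heterogeneous visit variances. A fully unstructured matrix would need 10 × 11 / 2 = 55 parameters from 40 participants.
- Use Kenward-Roger degrees of freedom.
- If a model does not converge, keep the random intercept and report cluster-robust standard errors by participant with a small-sample correction.

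The cost is a few lines of SAP text and some model terms, with no new data and no change in sample size. The downsides are possible non-convergence, which the fallback covers, and somewhat wider V11 CIs in some cases.

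### The primary model, fitted as written, gives both groups one variance in a 40 vs 20 comparison on a score capped at 100%; if training works, the primary 95% CI can be too narrow

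*SAP*

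**What the plan says.** Section 1.1 of the SAP randomises 1:1:1 to three arms and stratifies on the pre-assessment n-back score, with a cut at 87% correct (the upper stratum is "those scoring > 87% correct"). The primary comparison pools the two training arms. Section 1.4 therefore plans for "40 participants for the cognitive training groups" "and 20 participants for the PMR group".

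The primary outcome (section 4.1) is the percentage of correct n-back responses at post-assessment, which cannot exceed 100. Section 6.1 models the post and follow-up percentages with fixed effects for group, time point and task difficulty, covariates for pre-assessment score, age and sex, and a random intercept per subject. The result is stated thus: "The primary outcome (immediate transfer effects at post-assessment) will be estimated via marginal means (95% CI) from this model". The section mentions no group-specific variance, robust standard error or variance check.

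The repeated-measures training vs PMR models in section 6.2 have the same form, for example for the letter updating task: "Fixed effects will include group (cognitive training vs. PMR) and measurement time point (post vs. follow-up"). The last paragraph of 6.2 adds, for all analyses, that the link function depends on the scale of the outcome, and that skewed continuous data will be suitably transformed. It names neither a transformation nor a trigger.

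**The concern.** A linear mixed model with a plain random intercept has, by default, one random-intercept variance and one residual variance shared by both groups. With equal group sizes this does little harm to a difference in means. At 2:1 the larger group dominates the pooled variance, while the smaller group contributes most of the true variance of the difference. If the larger group is the less variable one, the standard error is understated.

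The SAP's own hypothesis points in that direction. Training is expected to raise the score, the score has a cap, and the trained group is the larger one. The primary effect could therefore be reported with too much precision exactly when there is an effect. This matters because section 1.4 says the trial will inform the sample size of a later multicenter trial.

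This is a between-group matter. It arises even with one value per person and is separate from the choice of within-person correlation structure.

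**Working it through.** **1. The plan's own figure.** Inputs from section 1.4: "we estimated an effect size of Cohen's d = 0.8"; "two-sided significance level of $\alpha = 0.05$ and a power of at least 80%, 60 participants are required"; groups of 40 and 20. The noncentrality is 0.8 × √(40 × 20 / 60) = 2.92 on 58 degrees of freedom, which gives power of 81.9%. At 2:1, a PMR group of 19 gives 79.9% and one of 20 gives 81.9%, so N = 60 reproduces. The pooled t-test is a planning formula and is not at fault.

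**2. Coverage with a pooled variance at 40 vs 20.** Let r = SD(training)/SD(PMR), with SD(PMR) = 1.
- True variance of the difference: r²/40 + 1/20.
- Variance the pooled method expects: [(40r² + 20)/60] × (1/40 + 1/20).
- Coverage ≈ 2Φ(1.96 × √(pooled/true)) − 1.

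| r | True | Pooled | SE ratio | Coverage |
|---|---|---|---|---|
| 1.0 | 0.0750 | 0.0750 | 1.00 | 95.0% |
| 0.9 | 0.0703 | 0.0655 | 0.97 | 94.2% |
| 0.8 | 0.0660 | 0.0570 | 0.93 | 93.2% |
| 0.7 | 0.0623 | 0.0495 | 0.89 | 92.0% |
| 0.6 | 0.0590 | 0.0430 | 0.85 | 90.6% |
| 1.4 | 0.0990 | 0.1230 | 1.11 | 97.1% |

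Simulated normal data agree for r of 0.6-0.8 (93.1%, 92.0% and 90.5% at 0.8, 0.7 and 0.6). Separate variances give 95.0% at all three. If training instead spreads the scores (r above 1), the interval is too wide.

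**3. How far a ceiling could push r.** The documents do not fix this, so two kinds of score were assumed and simulated at d of 0.7-0.8.
- *Binomial-type scores* (percent correct on a logit scale, mostly 60 trials per level, PMR mean 79-87%, SD 8-12): r is 0.58-0.76 and coverage mostly about 89-93%. With a PMR mean near 92% it is 88-91%. Values of 87-88% occurred in a mixed model with a group-by-time term and large variation between occasions; these partly reflect the random-intercept structure.
- *Normal score censored at 100* (mean 80-90%, SD 6-12): r is 0.75-0.97 and coverage about 93-95%.

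**4. Smaller or no effects (binomial-type scores).** Coverage was 93.4% at d of about 0.4 in one check. Another gave 92.6-94.3% at about 0.46 and 94.1-94.4% at 0.2-0.25. With no effect the groups have equal variances, and coverage was 95.3%.

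**5. Transformation.** In three binomial-type settings, the raw score with pooled variance gave 90.0-92.2%. The arcsine scale gave 93.2-94.1% and the logit scale 95.4-96.1%, each on its own scale.

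**6. A variance estimate that allows unequal groups.** HC2 standard errors gave mostly 93-95% for binomial-type scores (92.5% at the strongest ceiling) and about 94-96% for censored-normal scores.

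Limits: complete data, no strata and no imputation. HC2 was tested in an ANCOVA; CR2 within the full mixed model was not simulated.

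**The case against.** The strongest reply is that nothing in the SAP fixes the SD ratio. There is no mean, SD, ceiling share or number of n-back trials. A reader might infer that coverage will be about 90-92%, but the documents do not support that. It needs a ratio of roughly 0.55-0.70, and a normal score with a plain ceiling stays at 93-95%. A reader might also take the 87% cut as proof that many participants start near the cap. It is only a stratum threshold; the SAP does not say how many score above it. And d = 0.8 was taken from studies of the trained task, while the primary outcome is an untrained one, so a smaller effect and a smaller shortfall are quite possible. All of this stands, and it is why the size is given as a range.

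Second, equal variance is a default of the model, not a statement in the SAP, and the closing rule of 6.2 would allow a transformation. A logit scale does restore coverage. This stands only in part: the rule does not say which transformation applies, when, or whether the primary score is meant. It does not address unequal variances, and arcsine does less than logit. A transformed contrast is also no longer in percentage points.

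Third, a reader might extend the finding to every training vs PMR model in 6.2. The 2:1 weakness is shared, but no ceiling or direction is established for those outcomes, and those analyses are exploratory.

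**Conclusion.** The point holds as a conditional one. Fitted as written, the primary model pools variances in a 40 vs 20 comparison on a capped score, and its 95% CI can be too narrow if training raises scores. By arithmetic alone, coverage is about 93%, 92% and 91% at SD ratios of 0.8, 0.7 and 0.6. At d of 0.7-0.8, under the score distributions assumed above, it is mostly 89-93% (binomial-type) or 93-95% (censored normal), and it moves towards 95% as the effect shrinks.

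It would be wrong to read this as an inflated type I error: under the strict null the variances are equal and this mechanism is absent. The stated power reproduces and is not in question. The gain from a change is a sounder primary interval at almost no cost.

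**What to change.** In section 6.1, state that the primary CI and test use subject-clustered CR2 standard errors with Satterthwaite-type degrees of freedom, or let the random-intercept and residual variances differ by group. State also how this combines with the link and transformation rule at the end of 6.2: whether that rule applies to the primary score and, if so, which transformation and on what trigger. Either option can be combined with the planned multiple imputation.

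The same standard errors can serve the exploratory training vs PMR models in 6.2. Sleep efficiency is the exception. It has one post value per person, so random-intercept and residual variances cannot be separated. Use HC2-type robust standard errors there, or a single residual variance per group.

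The cost is a sentence or two in the SAP and a model option. With equal variances the interval is very slightly wider (simulated half-width 3.91 against 3.90 points). With unequal variances of the kind feared here it is wider: in one simulated setting at d = 0.81, the model-based half-width was 3.1 points where about 3.5 was needed. Under a strong ceiling, coverage may still stay slightly below 95%, at about 92.5-94%.
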